7 ADVERSE EVENTS AND TOXICITY MANAGEMENT

7.1 Definition of Adverse Events, Adverse Reactions, and Serious Adverse Events

7.1.1 Adverse Events

An adverse event (AE) is any untoward medical occurrence in a clinical study subject which does not necessarily have a causal relationship with the medicinal product. An AE can be any unfavorable and/or unintended sign, symptom, or disease temporally associated with the use of a medicinal product whether or not considered related to the medicinal product. AEs may also include pre or post treatment complications that occur, as a result of protocol specified procedures, lack of efficacy, over dose, drug abuse/misuse reports, or occupational exposure. Preexisting events that increase in severity or change in nature during or as a consequence of participation in the clinical study will also be considered AEs.

An AE does not include the following:

- Medical or surgical procedures such a surgery, endoscopy, tooth extraction, and transfusion. The condition that led to the procedure may be an adverse event and must be reported.
- Preexisting diseases, conditions, or laboratory abnormalities present or detected before the screening visit that do not worsen.
- Situations where an untoward medical occurrence has not occurred (e.g., hospitalization for elective surgery, social or convenience admissions)
- Overdose without clinical sequalae (see Section 7.6.1)
- Any Medical condition or clinically significant laboratory abnormality with an onset date before the consent form is signed and not related to a protocol associated procedure is not an AE. It is considered to be preexisting and should be documented in the medical record.

7.1.2 Serious Adverse Events

A serious adverse event (SEA) is defined as an event that, at any dose, results in the following:

- Death
- Life-threatening event in which the subject is at risk of death at the time of event. It does not refer to an event that hypothetically might have caused death if it were more severe.
- Inpatient hospitalization or prolongation of an existing hospitalization
- Persistent or significant disability/incapacity
- Congenital anomaly/birth defect in offspring of study subject born after subject received study drug
- A medically important event or reaction that may not immediately result in death, hospitalization, or life-threatening event but may jeopardize the subject or may require intervention to prevent an SAE from occurring. Medical and scientific judgement must be exercised to determine whether such an event is reportable under expedited reporting rules. Examples of this type of occurrence would include intensive treatment for allergic bronchospasm, blood dyscrasias or convulsions that do not result in hospitalization, development of drug dependency/abuse. For the avoidance of doubt, infections resulting from contaminated medical product will be considered a medically important event and subject to expedited reporting requirements.

7.1.3 Clinical Laboratory Abnormalities and Other Abnormal Assessments as Adverse Events or Serious Adverse Events

Laboratory abnormalities (e.g., clinical chemistry, hematology, and urinalysis) that require medical or surgical intervention or lead to study drug interruption, modification or discontinuation must be recorded as an AE or SAE. In addition, laboratory or other abnormal assessments (e.g., EKG, x-rays, and vital signs) that are associated with signs and/or symptoms must be recorded as an AE or SAE if they meet the definition detailed in Sections 7.1.1 and 7.1.2. If the laboratory abnormality is part of a syndrome, record the syndrome or diagnosis, not the laboratory result (i.e. "anemia," not "decreased hemoglobin").

For specific information on handling of clinical laboratory abnormalities in this study, please refer to Section 7.5.

7.2 Assessment of Adverse Events

The investigator or qualified sub-investigator is responsible for assessing AEs and SAEs for causality and severity as well as for final review and confirmation of accuracy of event information and assessments.

7.2.1 Assessment of Causality for Study Drugs and Procedures

The investigator or qualified sub-investigator is responsible for assessing the relationship to the study drug using clinical judgement and the following considerations:

- **No:** Evidence exists that the adverse event has an etiology other than the study drug. For SAEs, an alternative causality must be provided (e.g., preexisting condition, underlying disease, intercurrent illness, or concomitant medication).
- Yes: There is reasonable possibility that the event may have been caused by the study drug.

It should be emphasized that ineffective treatment should not be considered as causally related in the context of adverse reporting.

The relationship to study procedures (e.g., invasive procedures such as venipuncture) should be assessed using the following considerations:

- No: Evidence exists that the adverse event has an etiology other than the study procedure.
- Yes: The adverse event occurred, as a result of protocol procedures.

7.2.2 Assessment of severity

AE severity should be recorded and graded according to the Grading Scale for Severity of Adverse Events and laboratory Abnormalities (Appendix 2). For AE associated with laboratory abnormalities, the event should be graded on the basis of the clinical severity in the context of the underlying conditions; which might not be in agreement with the grading of the laboratory abnormality.

The distinction between the seriousness and the severity of an AE should be noted. Severe is a measure of intensity; a severe reaction is not necessarily a serious reaction. For example, a subject might have a headache that is described as severe but would not be considered a SAE unless it met one of the criteria for serious events.

7.3 Adverse Events and Serious Adverse Events

7.3.1 Adverse Events

Following initiation of study medication, all AEs regardless of cause or relationship until end of study must be reported to the study database.

All AEs should be followed up until resolution/return to baseline or until the adverse event is stable, if possible.

7.3.2 Serious Adverse Events

All SAEs regardless of cause or relationship that occurs after the subject signs the informed consent and until the duration of the study, including the protocol defined follow-up period, must be reported. This also includes any SAEs resulting from protocol associated procedures performed after informed consent is signed.

Investigators are not obligated to actively seek SAEs after the protocol defined follow up period; however, if the investigator learns of any SAEs that occur after study participation has concluded and the event is deemed relevant to the use of the study drug, they should promptly document and report the event.

7.4 Toxicity Management

All clinical events and clinically significant laboratory toxicities will be managed according to uniform guidelines detailed in Appendix 2 and as outlined below.

• Clinical events and clinically significant laboratory abnormalities will be graded according to the Grading Scale for Severity of Adverse Events and laboratory Abnormalities (Appendix 2).

Grade 3 and 4 clinically significant laboratory abnormalities should be confirmed by repeat testing
within 7 calendar days of receiving results and before study drug discontinuation, unless such a delay
is not consistent with good medical practice.

Any questions regarding toxicity management should be directed to the Investigator.

7.4.1 Grades 1 and 2 Clinical Event or Laboratory Abnormality

Continue study drug at the discretion of the Investigator

7.4.2 Grade 3 Clinical Event or Laboratory Abnormality

For Grade 3 clinical event or clinically significant laboratory abnormality, study drug may be continued if the event is considered to be unrelated to study drug.

For a Grade 3 clinical event or clinically significant laboratory abnormality confirmed by repeat testing that is considered to be related to the study drug, study drug will be withheld until the toxicity returns to ≤ grade 2. When restarting study drug following resolution of the adverse event, the study drug should be restarted at full dose.

If following re-challenge with study drug a laboratory abnormality returns to ≥ Grade 3 and is considered to be related to the study drug, then the study drug will be permanently discontinued and the subject managed according to local practice. Recurrence of laboratory abnormalities considered unrelated to the study drug may not require permanent discontinuation.

7.4.3 Grade 4 Clinical Events or Laboratory Abnormality

For a Grade 4 clinical event or clinically significant laboratory abnormality confirmed by repeat testing that is considered to be related to the study drug, the study drug will be permanently discontinued and the subject managed according to local practice. The subject should be followed as clinically indicated until the laboratory abnormality returns to baseline or is otherwise explained, whichever occurs first.

A clinically significant Grade 4 laboratory abnormality that is not confirmed by repeat testing should be managed according to the algorithm for the new toxicity grade.

Study drug may be continued without dose interruption for a clinically non-significant Grade 4 laboratory abnormality (e.g., elevated CK after significant exercise or triglyceride elevation on a non-fasting specimen) or a clinical event considered unrelated to the study drug, but must be discussed with the Investigator.

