7.4.4 ALT Flare

Defined as: serum ALT > 10 x upper limit of normal (ULN) and > 2 times Day 1 value, confirmed with repeat testing within 3 days of original results receipt, with or without associated symptoms

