7.4.4.1 Management of ALT Flare

When initial results are received, schedule subject to return to the clinic as soon as possible (ideally within 3 days of initial blood draw). During the visit, in addition to redrawing blood for repeat CMP testing, clinical assessment of the subject will be performed. The assessment should include a physical examination and evaluation of the subject's mental status.

If ALT elevation is confirmed, the following labs should be performed: plasma HBV DNA, HBV serology (HBsAg and HBsAb), HAC IgM, HCV serology, quantitative HDV RNA.

Based on the results of the confirmatory tests, the following treatment modifications are recommended:

Elevated liver enzymes, normal or stable total bilirubin relative to Day 1

If ALT levels are elevated (as specified in Section 7.4.4) with normal or stable total bilirubin, the subject may remain on the study drug and should be monitored weekly until ALT levels return to normal or Day 1 level. During monitoring, if the ALT values remain persistently elevated, the Investigator considers whether the study drug should be discontinued.

Elevated liver enzymes, elevated total bilirubin

During monitoring, if the ALT values and the liver function tests remain persistently elevated, the Investigator should consider discontinuing the study drug.

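### For a confirmed, clinically significant, drug-related ALT flare, section 7.4.3 orders permanent discontinuation while 7.4.4.1 allows the subject to stay on drug if bilirubin is stable, and nothing says which governs

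*Combined protocol and SAP*

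**What the plan says.** Four parts of the protocol bear on this.

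- **Appendix 2, ALT row.** Grade 3 is 5.1 to 10 x ULN and Grade 4 is above 10 x ULN.
- **Section 7.4.3 (Grade 4).** For a "clinically significant laboratory abnormality confirmed by repeat testing that is considered to be related to the study drug, the study drug will be permanently discontinued". The same section names the cases in which drug may go on. One is laboratory-based: "Study drug may be continued without dose interruption for a clinically non-significant Grade 4 laboratory abnormality". The other is a clinical event judged unrelated. ALT flare is not among them.
- **Section 7.4.4 (ALT Flare).** A flare is "serum ALT > 10 x upper limit of normal (ULN) and > 2 times Day 1 value". The definition also sets a time limit on the second sample, since the value has to be "confirmed with repeat testing within 3 days of original results receipt".
- **Section 7.4.4.1 (Management of ALT Flare).** After a set of viral hepatitis tests, it says: "Based on the results of the confirmatory tests, the following treatment modifications are recommended". Two branches follow, split by bilirubin. With normal or stable bilirubin, "the subject may remain on the study drug and should be monitored weekly until ALT levels return to normal or Day 1 level", and during monitoring, "if the ALT values remain persistently elevated, the Investigator considers whether the study drug should be discontinued". With raised bilirubin, "if the ALT values and the liver function tests remain persistently elevated, the Investigator should consider discontinuing the study drug".

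**The concern.** Section 7.4.3 is mandatory and section 7.4.4.1 is permissive, and both reach the same subject when a flare is clinically significant and considered related to study drug. Two physicians with identical cases could act in opposite ways and each cite the protocol. The one who kept the subject on drug would be following the only flare-specific text while departing from the plain wording of 7.4.3. The event is a drug-related liver signal, where the stopping rule needs to be settled before the first case arises. The issue is subject safety and uniform conduct.

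**Working it through.** The plan gives no figure to reproduce. The check compares thresholds, then sets the instructions side by side.

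**1. Do the two definitions overlap?** In multiples of ULN, the flare threshold is max(10, 2 x Day 1 ALT) and the Grade 4 threshold is 10 (Appendix 2). Entry requires ALT of at most 5 x ULN (section 4.5.1).

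| Day 1 ALT (x ULN) | 2 x Day 1 | Flare threshold | Grade 4 threshold |
|---|---|---|---|
| 1 | 2 | 10 | 10 |
| 2 | 4 | 10 | 10 |
| 3 | 6 | 10 | 10 |
| 4 | 8 | 10 | 10 |
| 5 | 10 | 10 | 10 |
| 6 | 12 | 12 | 10 |
| 8 | 16 | 16 | 10 |

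A flare is always a Grade 4 value. For any subject whose Day 1 ALT is still within the entry limit, the twice-Day-1 condition adds nothing and the two thresholds coincide. They separate only if ALT has risen above 5 x ULN by Day 1.

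**2. Which flares meet the 7.4.3 trigger?** Those that are also clinically significant and considered related. Flares with evidence of another cause (section 7.2.1), such as viral hepatitis, fall outside it. So do clinically non-significant ones.

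**3. What do the two sections say for that set?**

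| Bilirubin | 7.4.3 | 7.4.4.1 |
|---|---|---|
| Normal or stable | Permanent discontinuation | May remain, weekly monitoring; discontinuation considered if ALT stays raised |
| Raised | Permanent discontinuation | Discontinuation to be considered if values stay raised |

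The first row is a direct conflict. The second is weaker: 7.4.4.1 gives no express permission to continue there, but it asks only for consideration where 7.4.3 requires stopping.

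**4. Does any text rank them?** No.
- The opening of 7.4 applies Appendix 2 and everything below it together, and sends questions to the Investigator.
- Section 7.4.3 does not mention 7.4.4 or 7.4.4.1, and they do not mention 7.4.3.
- Section 7.1.3 refers readers to 7.5 for laboratory abnormalities, but 7.5 is Hepatitis C Management.

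**5. Does timing matter?** Section 7.4 allows 7 calendar days from results for the repeat test, and 7.4.4 requires it within 3. The same ALT confirmed by day 3 comes under both texts. Confirmed on days 4 to 7, it is not a flare by definition and only 7.4.3 applies.

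**Worked case.** Day 1 ALT is 1 x ULN. On treatment, ALT is 12 x ULN, confirmed within 3 days, with stable bilirubin and negative viral tests, and is judged significant and related. The value exceeds both 10 x ULN and 2 x Day 1 (2 x ULN). Section 7.4.3 says permanent discontinuation; 7.4.4.1 says the subject may remain with weekly monitoring.

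**The case against.** The strongest reply is that a permission and a mandate can be read together. Section 7.4.4.1 only recommends, 7.4.3 commands, and stopping the drug satisfies both. On a sequential reading, 7.4.4.1 covers the work-up and 7.4.3 takes over once the event is judged related. Other text also limits the harm: section 6.2.2.5 requires discontinuation for unacceptable toxicity, 7.4.5 calls for a thorough work-up of suspected hepatobiliary toxicity, and 7.4 sends questions to the Investigator.

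Part of this stands. One course of action does comply with both texts, the set is narrow, and the raised-bilirubin branch is a difference in force rather than an outright contradiction. The 3-day and 7-day windows are not opposed in themselves, since a repeat by day 3 meets both. Nor can one say that continuing is wrong overall, because that would assume that 7.4.3 prevails.

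The core is not answered. The sequential reading is not written: the recommendations come after the confirmatory tests and are split only by bilirubin, not by cause. That the specific section overrides the general one is not written either, and it would leave a further question. Under 7.4.2 a confirmed, significant, related Grade 3 ALT requires drug to be withheld, while a higher, Grade 4 value could continue uninterrupted under 7.4.4.1. The backstops in 6.2.2.5 and 7.4.5 do not rank the two rules. Causality and severity may be assessed by sub-investigators (section 7.2), so uniform practice cannot be assumed from a single decision-maker.

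**Conclusion.** The point holds and should be corrected. The two sections give incompatible instructions for a flare that is confirmed within 3 days, clinically significant, drug-related and accompanied by normal or stable bilirubin. They also differ in force when bilirubin is raised. The conclusion rests only on the protocol's wording and the Appendix 2 threshold. No event rate is given in the documents and none is assumed, so the number of subjects affected among the approximately 100 planned cannot be stated. The weight given to the point comes from the consequence of an unclear stopping rule for a hepatic signal, not from its frequency. No effect on the primary endpoint is claimed.

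**What to change.** Reconcile sections 7.4.3 and 7.4.4.1 with Appendix 2, and in both sections state:

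- which one governs a confirmed, clinically significant, drug-related ALT above 10 x ULN, with and without raised bilirubin;
- whether the viral test results change that;
- which repeat-test window, 3 days or 7 calendar days, applies to ALT above 10 x ULN;
- whether 7.4.2 applies while a flare resolves through 5.1 to 10 x ULN.

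As a minor correction, point the 7.1.3 cross-reference to the governing toxicity section instead of 7.5. Which rule stands is for the sponsor's clinical team. The cost is a wording amendment, with no added tests, visits or subjects.

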7.4.4 ALT Flare

Defined as: serum ALT > 10 x upper limit of normal (ULN) and > 2 times Day 1 value, confirmed with repeat testing within 3 days of original results receipt, with or without associated symptoms

7.4.4.1 Management of ALT Flare

When initial results are received, schedule subject to return to the clinic as soon as possible (ideally within 3 days of initial blood draw). During the visit, in addition to redrawing blood for repeat CMP testing, clinical assessment of the subject will be performed. The assessment should include a physical examination and evaluation of the subject's mental status.

If ALT elevation is confirmed, the following labs should be performed: plasma HBV DNA, HBV serology (HBsAg and HBsAb), HAC IgM, HCV serology, quantitative HDV RNA.

Based on the results of the confirmatory tests, the following treatment modifications are recommended:

Elevated liver enzymes, normal or stable total bilirubin relative to Day 1

If ALT levels are elevated (as specified in Section 7.4.4) with normal or stable total bilirubin, the subject may remain on the study drug and should be monitored weekly until ALT levels return to normal or Day 1 level. During monitoring, if the ALT values remain persistently elevated, the Investigator considers whether the study drug should be discontinued.

Elevated liver enzymes, elevated total bilirubin

During monitoring, if the ALT values and the liver function tests remain persistently elevated, the Investigator should consider discontinuing the study drug.

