6.2.2.5 Criteria for Discontinuation of Study Treatment

Study Medication will be discontinued in the following instances

- Unacceptable toxicity, or toxicity that in the judgement of the investigator compromises the ability to continue study specific procedures or is considered to not be in the subject's best interest
- Subject request to discontinue for any reason
- Pregnancy during the study
- Development of active tuberculosis
- Discontinuation of the study at the request the IRB

Study medication may be discontinued in the following instances:

- Intercurrent illness that would in the judgement of the investigator affects assessments of clinical status to a significant degree. Following resolution of the intercurrent illness, the subject may resume study dosing at the discretion of the investigator.
- Lack of efficacy

Subject noncompliance

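### For a related, clinically significant ALT flare with stable bilirubin, 7.4.3 requires a permanent stop while 7.4.4.1 lets study drug continue, and no text says which governs

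*Combined protocol and SAP*

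**What the plan says.** Section 7.4.4 defines a flare as "serum ALT > 10 x upper limit of normal (ULN) and > 2 times Day 1 value", confirmed by a repeat test. Appendix 2 grades ALT above 10 x ULN as Grade 4.

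Section 7.4.3 covers a Grade 4 laboratory abnormality that is clinically significant and confirmed. If it is "considered to be related to the study drug, the study drug will be permanently discontinued and the subject managed according to local practice". The same section lets drug continue for a Grade 4 laboratory abnormality that is not clinically significant, "or a clinical event considered unrelated to the study drug, but must be discussed with the Investigator".

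Section 7.4.4.1 introduces its drug decisions with "Based on the results of the confirmatory tests, the following treatment modifications are recommended". It then splits by bilirubin:

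- Normal or stable bilirubin: "the subject may remain on the study drug and should be monitored weekly until ALT levels return to normal or Day 1 level". If ALT stays high, the Investigator considers whether to stop.
- Raised bilirubin: "During monitoring, if the ALT values and the liver function tests remain persistently elevated, the Investigator should consider discontinuing the study drug".

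Neither branch mentions causality. For comparison, section 7.4.2 says that for a confirmed, clinically significant Grade 3 abnormality considered related, "study drug will be withheld until the toxicity returns to" Grade 2 or lower.

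**The concern.** The same subject can fall under two rules with different outcomes. A site that follows 7.4.3 stops drug permanently. A site that follows 7.4.4.1 for the same related flare with stable bilirubin may keep dosing and monitor weekly.

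The permissive reading also reverses the order of severity. A related, confirmed, clinically significant ALT of 8 x ULN is Grade 3 and is withheld under 7.4.2. A related ALT of 12 x ULN with stable bilirubin could stay on drug. What is at stake is the handling of a subject with possible drug-induced liver injury. Investigators and qualified sub-investigators both assess causality (7.2), so consistent action depends on the text being clear.

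**Working it through.** The plan states no figure on this point, so the check sets the rules side by side.

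**1. Overlap.** Appendix 2 makes ALT > 10 x ULN Grade 4. A flare needs ALT > 10 x ULN, plus > 2 x the Day 1 value, plus confirmation. Every flare is therefore a confirmed Grade 4 abnormality.

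The overlap is close in the other direction too. Section 4.5.1 admits subjects with ALT up to 5 x ULN. If the Day 1 value respects that limit, 2 x Day 1 is at most 2 x 5 = 10 x ULN, so any ALT above 10 x ULN already meets the second condition. (Eligibility is judged at screening, so a Day 1 value could be higher.) If 7.4.4.1 displaced 7.4.3, little would be left of the mandatory stop for ALT.

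**2. Outcomes for a confirmed, clinically significant flare.**

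| Judged | Bilirubin | 7.4.3 | 7.4.4.1 | Result |
|---|---|---|---|---|
| Related | Normal or stable | Permanent stop | May continue | Express permission against a mandatory stop |
| Related | Raised | Permanent stop | Consider stopping if values persist | Tension; no express permission |
| Unrelated | Normal or stable | No rule stated | May continue | 7.4.4.1 fills the gap |
| Unrelated | Raised | No rule stated | Consider stopping if values persist | 7.4.4.1 fills the gap |

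The unrelated rows show no rule under 7.4.3 because its option to continue names only a non-significant laboratory abnormality or an unrelated clinical event. A clinically significant, unrelated laboratory flare is neither. Section 7.4.4.1 therefore has a proper use, and hepatitis B coinfected subjects are followed in this study (6.2.4.1), so flares with another cause can occur.

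**3. Search for a precedence rule.**

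- 7.4 applies Appendix 2 and its subsections together and does not rank them.
- 7.1.3 points to 7.5 for handling laboratory abnormalities, but 7.5 is Hepatitis C Management.
- 7.4.5 requires a work-up and gives no drug decision.
- 6.2.2.5 makes discontinuation mandatory for "Unacceptable toxicity, or toxicity that in the judgement of the investigator compromises the ability to continue study specific procedures", but what qualifies is largely a matter of judgement.

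None of these decides between 7.4.3 and 7.4.4.1.

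**4. Size.** The documents give no rate of related flares. Assuming 0.1% to 1% of subjects, the expected number at n = 100 is 100 x 0.001 = 0.1 to 100 x 0.01 = 1.

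**5. Effect on efficacy tables.** Under the snapshot algorithm (8.5.1.1), take a subject who stops for toxicity with last on-treatment HIV-1 RNA below 50 copies/mL and no on-treatment Week 48 result. That subject counts as having no virologic data. This lowers the proportion below 50 copies/mL by 1/100 = 1 percentage point and leaves the primary proportion (at or above 50 copies/mL) unchanged.

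**The case against.** The strongest reply is that the sections are compatible as written. The 7.4.3 rule is mandatory and 7.4.4.1 is a permissive recommendation, so stopping drug for a related flare satisfies both. The 7.4.4.1 work-up is for viral hepatitis, which suggests the section was meant for flares with another cause. Toxicity questions go to the Investigator, and unacceptable toxicity must stop treatment anyway.

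Most of this stands as the sensible reading. It does not remove the point, because that precedence is not written. The reading that a specific section overrides a general one is just as available and leads to the opposite action. Referral to the Investigator names a decision-maker, not a rule.

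A reader might infer three stronger claims that the documents do not support:

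- *Raised bilirubin is a second direct contradiction.* That branch never says the subject may remain on drug. Continuation is at most implied by the reference to monitoring.
- *Raised bilirubin together with a flare is treated more leniently than raised bilirubin alone.* That holds only if 7.4.4.1 switches off 7.4.2 and 7.4.3, which is the unresolved question itself.
- *No evidence on another cause exists until a flare is confirmed.* Hepatitis C antibody, and hepatitis B serology where immunity is undocumented, are taken at screening (6.2.4.1). Appendix 1 schedules hepatitis B viral load from Week 4 to Week 48 in coinfected subjects.

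**Conclusion.** The point holds in a limited form. There is one direct conflict: a confirmed, clinically significant flare considered related, with normal or stable bilirubin. There is also an unresolved tension when bilirubin is raised. Flares judged unrelated raise no conflict, and a flare that is not clinically significant may continue under 7.4.3 in any case.

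The conclusion rests on the text alone. The only assumption is the 0.1% to 1% rate, which affects how often the conflict would arise and not whether it exists. The event is rare and the efficacy consequence small, so this is a safety clarification that should be made, not a threat to the trial's results.

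A reader might also infer that drug must be held while causality is being decided. The documents do not support making that compulsory. Section 6.1.3 prohibits any other HIV medication, so a hold interrupts all HIV treatment. That trade-off belongs to the sponsor's medical lead.

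**What to change.** In 7.4.4.1, state that both bilirubin branches apply only to flares not considered related to study drug, and that a confirmed, clinically significant flare considered related is managed under 7.4.3. Add a matching cross-reference in 7.4.3.

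The cost is a wording change in two sections, with no new test or visit. The downside is that an occasional subject with a related flare will stop drug who might have continued.
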